## 12.4 Investigators, Investigational Sites and IRBs

Only investigators qualified by training and experience to perform a clinical investigation are selected. Sponsor or designee will contact and select all principal investigators (legally responsible party(ies) at each investigational site), who, in turn, will select their staff.

A list of active Investigator names, sub-investigator names, Institution names/ addresses and reviewing IRBs names/addresses is maintained by Sponsor, external to the protocol.

## 12.5 Central Organizations and/or Vendors

A list of names and addresses of organizations and/or vendors involved in patient management and associated testing and analysis where it affects the validity of the investigation is maintained by Sponsor, external to the protocol

## **13 LIST OF ABBREVIATIONS**

Term	Definition
AE	Adverse event
ALCMI	Addario Lung Cancer Medical Institute
AOM	Age of Majority
CDMS	Clinical Data Management System
CRF	Case Report Form
CRO	Clinical Research Organization
CSR	Clinical Study Report
eCRF	Electronic Case Report Form
EDC	Electronic Data Capture
EMG	Electromyography
ICH/GCP	International Conference on Harmonisation / Good Clinical Practices
HIPAA	The Health Insurance Portability and Accountability Act of 1996
Нх	History
IRB/IEC	Institutional Review Board / Independent Ethics Committee
kg	Kilogram
LEMS	Lambert-Eaton myasthenic syndrome
Q3m	Every three months
SCLC	Small Cell Lung Cancer
VGCC Ab	Voltage-gated calcium channel antibody test

## 15.2 Appendix 2: LEMS Symptom Directed Neurological Evaluation

Paraneoplastic syndromes are clinical syndromes characterized by a recognizable grouping of signs and symptoms in patients with cancer. They affect about 1 in 10 patients with lung cancer, including small cell lung cancer (SCLC). Detecting them early can help improve patients' lives. The following symptoms are most commonly associated with LEMS

- · recent muscle weakness on both sides of the body or a heaviness in legs or
- · recently experienced difficulty getting up from a chair?
- · recently experienced dry eyes, dry mouth, or constipation?

Is the patient experiencing any of the signs and symptoms of LEMS?
☐ YES Continue to the next 2 questions
NO This survey is complete, schedule the subject for the next visit
If this subject was not participating in this study, based on the review of the
subject symptoms would you have normally ordered a VGCC Ab test?
☐ YES
□ NO
Do you consider this subject's neurologic symptoms suggestive of having LEMS?
YES Complete page 2 of this survey to describe the symptoms observed.
☐ NO This survey is complete, schedule the subject for the next visit
Signature of person completing this form:

Version 1 28May2025 Page 1 of 2

Page 2 of 2

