## 1 INTRODUCTION

## 1.1 Background

Lambert-Eaton Myasthenic Syndrome (LEMS) is a rare auto-immune presynaptic disorder of the neuromuscular junction (NMJ) associated with proximal muscle weakness, reduced or absent muscle stretch reflexes, and autonomic dysfunction (PMID: 4330759). Up to 60% of cases occur in the setting of a paraneoplastic disorder, with small-cell lung cancer (SCLC) being the most common tumor type (PMID: 21245427; 2838124; 15277653). Antibodies (Ab) against voltage-gated calcium channels (VGCC), particularly of the P/Q type, are identified in 85-90% of patients with LEMS (PMID: 9668336; 7739683; 9094058). Antibodies to N-type and L-type VGCC have also been reported in 25-40% of LEMS, concurrently with the P/Q-type antibodies, where (PMID: 8309586; 8583238), while few cases are seronegative.

Awareness of the clinical features, diagnostic evaluation, malignancy workup, and management of LEMS, as well as a high index of suspicion, are important for timely diagnosis and proper treatment. When LEMS is suspected or diagnosed, the evaluation of a primary malignancy, particularly SCLC, is warranted due to the strong association. A diagnosis of SCLC has been established within 1 year of LEMS diagnosis in 96% of patients (PMID: 18779614). Treatment of the underlying malignancy may be the only intervention necessary to improve neurologic symptoms.

In the context of LEMS associated with SCLC, the median survival is approximately 18 months. Median survival in individuals with SCLC and LEMS is better than those with only SCLC (median survival of 17 vs 7 months). This longer survival was seen in both limited SCLC (median survival of 19 vs 12.1 months) and extensive SCLC (13 vs 4.9 months). Individuals with non–tumor–associated LEMS have a similar life expectancy to the general population.

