# SYMPTOM DIRECTED NEUROLOGICAL EVALUATION

Site #:		Subject #	024-			
Visit:	□Enrollment □3 month □6 month □9 month	Date of visit:				
$oxed{oxed}$	□12 month □ Other	(dd/mmm/w)				
Indicat	Indicate the symptoms the subject has which are suggestive of having LEMS.					
(check all that apply)						
	Dry eyes, drooping eyelids, and/or blurred vision					
	Proximal Arm (muscle weakness), difficulty raising arms or lifting objects					
	Proximal Leg (muscle weakness), upper leg weakness or lower leg weakness					
	Absent deep tendon reflexes					
	Distal leg (muscle weakness)					
	Post Exercise facilitation					
	Dry Mouth, difficulty swallowing					
	Orthostatic Hypotension, dizziness upon standing					
	Constipation					
☐ Impotence, erectile dysfunction						
In som	ne patients, a waddling gait may be indi	cative of LEI	MS			
(check th	ne box that best describes their gait)					
	Patient walks with a waddling gait		□ 2.5€ 5.			
	Patient does not walk with a waddling	gait	Use the QR code to watch a classic example of "LEMS gait			
Document any other symptoms noted for this subject.						
1	If the subject's neurological symptoms are suggestive of having LEMS, review along with the					
	VGCC Ab results.					
☐ If the subject is BOTH neurologically suggestive of having LEMS and the VGCC Ab test is						
1.	positive, then the subject is considered as Clinically Suspicious of a LEMS Diagnosis as defined					
in the protocol. The subject has met the criteria to complete the study. Complete the End of Study visit for the subject including the Investigator Course of Action Form.						
☐ If the VGCC antibody test is negative , the subject does not meet the criteria to complete the						
study. Schedule the subject for the next study visit in 3 months.						
	☐ End of study ☐ Next visit scheduled					
Signature of person completing this form:						

Version 1 28May2025

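### The page 1 question that can end the LEMS symptom evaluation is prompted by a shorter symptom list than page 2 uses, so a narrow reading could lose primary-endpoint cases

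*Protocol*

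**What the plan says.** Page 1 of Appendix 2 introduces its list with "The following symptoms are most commonly associated with LEMS". Three bullets follow: "recent muscle weakness on both sides of the body or a heaviness in legs or" (the bullet breaks off there in the text available, so a word or more may be missing); "recently experienced difficulty getting up from a chair"; and "recently experienced dry eyes, dry mouth, or constipation". The form then asks "Is the patient experiencing any of the signs and symptoms of LEMS". The negative answer carries the instruction "NO This survey is complete, schedule the subject for the next visit". The later question, whether the symptoms suggest LEMS, is reached only after a YES.

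Page 2 is completed only once the symptoms have been judged suggestive. Its checklist includes "Absent deep tendon reflexes" and other items that page 1 does not show. Section 1.1 describes LEMS as "associated with proximal muscle weakness, reduced or absent muscle stretch reflexes, and autonomic dysfunction".

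Under Sections 3.1 and 4.3, a clinically suspicious case needs both a suggestive neurological evaluation and a positive VGCC antibody. Section 7.3.3 lets a delegated individual make the suggestive determination; the investigator then completes page 2. Under Section 7.3.4 the blood is drawn within 15 days of the visit. If the result is positive, the investigator checks whether the evaluation was suggestive.

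**The concern.** The first question on page 1 controls the symptom half of the primary endpoint, and the fuller list comes after the exit. A rater who takes the three bullets as the working definition would answer NO for a subject with, say, absent reflexes and dizziness on standing.

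No step at that visit corrects this. A positive antibody leads only to a review of the evaluation already completed, and Section 7.3.4 specifies no re-examination. A NO on page 1 also leaves no item-level symptom data, so such misses could not be found or adjusted for in the analysis.

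The error runs one way. It lowers the observed incidence, against the Synopsis hypothesis that incidence exceeds about 3%, and the same data feed the Part A futility review. If sites read the question differently, ascertainment also varies by site.

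**Working it through.** **1. The two pages side by side**

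| Page 2 feature | Among the page 1 prompts? | Named in Section 1.1? |
|---|---|---|
| Proximal arm or leg weakness | Yes, in substance | Yes |
| Distal leg weakness | Arguably, under weakness or heavy legs | No |
| Dry eyes, dry mouth, constipation | Yes | By implication (autonomic) |
| Drooping eyelids or blurred vision | No | No |
| Difficulty swallowing | No | No |
| Orthostatic hypotension or dizziness | No | By implication (autonomic) |
| Erectile dysfunction | No | Not by name |
| Waddling gait | No | No |
| Absent deep tendon reflexes | No | Yes |
| Post-exercise facilitation | No | No |

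Seven features are on page 2 but not among the page 1 prompts. The background supports reflexes explicitly and orthostatic symptoms by implication. The eyelid or vision item and gait rest on page 2 alone.

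**2. What a NO does**

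NO on page 1 → no suggestive judgement at that visit → the first half of the endpoint definition is not met → no case at that visit, whatever the antibody result. The subject returns in 3 months.

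**3. The plan's own figure**

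Section 4.1: N = 400, incidence 3%. Expected cases = 400 × 0.03 = 12.0, which reproduces the stated figure of about 12. The exact (Clopper-Pearson) 95% interval for 12/400 is 1.6% to 5.2%.

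**4. Illustration of loss**

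Let *s* be the share of true cases captured at any visit, after any recovery at later visits. The protocol gives no value, so *s* is an assumption.

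Expected cases = 400 × 0.03 × *s*; observed incidence = 3% × *s*; true incidence that would be observed as 3% = 3% / *s*.

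| *s* (assumed) | Expected cases | Observed incidence | True incidence observed as 3% |
|---|---|---|---|
| 100% | 12.0 | 3.0% | 3.0% |
| 95% | 11.4 | 2.85% | 3.2% |
| 90% | 10.8 | 2.7% | 3.3% |
| 80% | 9.6 | 2.4% | 3.75% |
| 50% | 6.0 | 1.5% | 6.0% |

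At 95% to 80% capture, 0.6 to 2.4 cases are lost and the estimate falls by 0.15 to 0.6 percentage points. The exact interval reaches 1.4 points below 3.0% and 2.2 points above it, so the shift lies within sampling error. Unlike sampling error, it does not shrink with more subjects.

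**5. Could site differences be seen in the data?**

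Section 3.2 expects about 40 subjects per site: 40 × 0.03 = 1.2 expected cases per site. Differences in how sites read the question could not be told from chance at that count.

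**The case against.** The strongest reply is that the question is open. The bullets are presented as the most common symptoms, not the only ones, and the question covers any sign or symptom. A subject with drooping eyelids or a waddling gait qualifies for YES as the form stands. This reply is right. A reader might infer that the form excludes subjects whose features appear only on page 2, or that raters cannot see page 2 before answering. Neither is supported: nothing restricts YES to the bullets, and Appendix 2 is one two-page form with nothing withheld. What remains is the risk of a narrow reading.

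A second reply is that the evaluation is repeated every 3 months, so a NO is not final. This also stands, with limits. A repeat uses the same page 1, and Section 7.2 prefers the same individuals to perform a subject's evaluations, so a narrow reading may recur. Within Part A, visits are suspended at around month 12, so a subject enrolled after month 9 has no quarterly visit before then.

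A third reply is that page 2 documents symptoms and does not decide the endpoint, so a short prompt before a fuller record suits a brief evaluation. The lists need not be identical. But the prompt decides who reaches the suggestive judgement, so it should not steer raters away from features the form itself treats as suggestive.

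Finally, a lost case needs several things together: a positive antibody, none of the page 1 symptoms, a narrow reading, remaining features that would have been judged suggestive, and no later capture. That is why the size is left open.

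**Conclusion.** The point holds as a weakness in how the primary endpoint is ascertained. A NO on page 1 rules out a case at that visit, and the prompts before it omit seven features that page 2 records as suggestive. If raters read the prompts narrowly, incidence is biased downward and may differ by site, without a trace in the data.

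The size is unknown. The 0.6 to 2.4 lost cases, and the fall from 3.0% to between 2.85% and 2.4%, rest entirely on an assumed permanent loss of 5% to 20%, which has no source in the protocol.

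Two stronger conclusions a reader might draw do not follow. It is not shown that affected subjects can never become cases, because later visits can capture them. Nor does the background list all the missing features: it names neither eye signs nor gait, and dry eyes is already on page 1.

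**What to change.** Revise page 1 of Appendix 2:

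- Add to the prompt the page 2 items that can be asked or observed without further examination: drooping eyelids or blurred vision, difficulty swallowing, dizziness on standing, erectile dysfunction and waddling gait.
- Add absent reflexes and post-exercise facilitation, marked *if known or examined*, so that no examination is added for every subject at every visit.
- Word the question as *any of these or any other signs or symptoms of LEMS*. Limiting it to the listed items would close a question that is now open and would shut out features page 2 can still take as free text.

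The later judgement of whether the symptoms suggest LEMS stays unchanged, and so does the endpoint definition.

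The cost is a one-page form revision and a short notice to sites. Page 1 becomes slightly longer and more subjects will answer YES at the first question; the suggestive judgement still filters them. The change makes a narrow reading less likely but does not create item-level data for subjects who answer NO.

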# SYMPTOM DIRECTED NEUROLOGICAL EVALUATION

Site #:		Subject #	024-			
Visit:	□Enrollment □3 month □6 month □9 month	Date of visit:				
$oxed{oxed}$	□12 month □ Other	(dd/mmm/w)				
Indicat	Indicate the symptoms the subject has which are suggestive of having LEMS.					
(check all that apply)						
	Dry eyes, drooping eyelids, and/or blurred vision					
	Proximal Arm (muscle weakness), difficulty raising arms or lifting objects					
	Proximal Leg (muscle weakness), upper leg weakness or lower leg weakness					
	Absent deep tendon reflexes					
	Distal leg (muscle weakness)					
	Post Exercise facilitation					
	Dry Mouth, difficulty swallowing					
	Orthostatic Hypotension, dizziness upon standing					
	Constipation					
☐ Impotence, erectile dysfunction						
In som	ne patients, a waddling gait may be indi	cative of LEI	MS			
(check th	ne box that best describes their gait)					
	Patient walks with a waddling gait		□ 2.5€ 5.			
	Patient does not walk with a waddling	gait	Use the QR code to watch a classic example of "LEMS gait			
Document any other symptoms noted for this subject.						
1	If the subject's neurological symptoms are suggestive of having LEMS, review along with the					
	VGCC Ab results.					
☐ If the subject is BOTH neurologically suggestive of having LEMS and the VGCC Ab test is						
1.	positive, then the subject is considered as Clinically Suspicious of a LEMS Diagnosis as defined					
in the protocol. The subject has met the criteria to complete the study. Complete the End of Study visit for the subject including the Investigator Course of Action Form.						
☐ If the VGCC antibody test is negative , the subject does not meet the criteria to complete the						
study. Schedule the subject for the next study visit in 3 months.						
	☐ End of study ☐ Next visit scheduled					
Signature of person completing this form:						

Version 1 28May2025

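### Page 2 of the symptom form lets lower-leg weakness be recorded as proximal, distal or both, and merges autonomic with ocular or bulbar signs; this blurs the exploratory symptom analyses but not the case count

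*Protocol*

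**What the plan says.** Section 1.1 describes LEMS as "associated with proximal muscle weakness, reduced or absent muscle stretch reflexes, and autonomic dysfunction". Appendix 2 turns this into a two-page form.

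Page 1 lists prompts, among them "recently experienced dry eyes, dry mouth, or constipation". It then asks for one yes/no on whether any such symptom is present, whether a VGCC test would normally have been ordered, and whether the rater finds the symptoms suggestive of LEMS. Page 2 is filled in only after a yes to that last question.

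Three page 2 boxes matter here:

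- The proximal leg box reads "Proximal Leg (muscle weakness), upper leg weakness or lower leg weakness". A separate box reads "Distal leg (muscle weakness)".
- The eye box reads "Dry eyes, drooping eyelids, and/or blurred vision".
- The mouth box reads "Dry Mouth, difficulty swallowing".

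Page 2 also has single-concept items, such as "Proximal Arm (muscle weakness), difficulty raising arms or lifting objects" and a gait item with the option "Patient walks with a waddling gait", and a free-text line.

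Under sections 3.1, 4.3, 7.3.3 and 7.3.4, a case needs the suggestive judgement and a positive VGCC antibody test. Section 4.3 plans descriptive analysis and exploratory correlations across all variables, including the neurological evaluation, the antibody result and its subtypes.

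**The concern.** The leg items contradict each other. One files lower-leg weakness under proximal, and the other offers a distal category without saying where proximal ends. Two raters at different sites could see the same subject, follow the form correctly and record different things. Proximal weakness is the first feature in the protocol's own description of LEMS, so this is an unfortunate item to leave ambiguous.

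The eye and mouth boxes have a different fault. Each is double-barrelled, and a tick does not show whether the autonomic symptom, the ocular or bulbar sign, or both were present.

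The loss occurs at data capture, so no later analysis can undo it. Page 2 is the only itemised symptom record, because page 1 does not store which symptom led to the yes. A subject who becomes a case goes to the End of Study visit, where only the intended course of action is recorded. The study therefore collects no electrophysiology result on new cases that could later show the symptom pattern.

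**Working it through.** **Inputs.** The 11 page 2 items in Appendix 2 (10 symptom boxes plus the gait item); the target of up to 400 subjects and the 3% incidence in section 4.1; the case definition in section 4.3.

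**The plan's own figure.** 400 × 0.03 = 12, which agrees with the roughly 12 cases stated in section 4.1.

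**Item audit.** Each item is classed by whether a tick points to one kind of feature or to more than one.

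| Item | A tick can mean | Mixed? |
|---|---|---|
| Proximal leg | proximal or lower-leg weakness | yes |
| Eye box | autonomic or ocular | yes |
| Mouth box | autonomic or bulbar | yes |
| Proximal arm | proximal weakness | no |
| Distal leg | distal weakness | no |
| Absent reflexes | reflex sign | no |
| Post-exercise facilitation | facilitation | no |
| Orthostatic hypotension | autonomic | no |
| Constipation | autonomic | no |
| Impotence | autonomic | no |
| Gait | proximal pattern | no |

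Mixed: 3 of 11. Unmixed: 11 − 3 = 8 of 11.

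**What each mixed box loses.**

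- Leg: lower-leg-only weakness has three valid records (proximal box, distal box, both). Conversely, a tick in the proximal leg box alone may mean upper leg, lower leg or both.
- Eye: with three signs in one box, 2³ − 1 = 7 different combinations give the same tick.
- Mouth: with two signs, and reading the comma as *or*, 2² − 1 = 3 combinations give the same tick.

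**Which records stay readable.** Constipation only, distal leg only, and proximal arm weakness with a waddling gait can all be separated. A record is ambiguous when its evidence lies only in the mixed boxes, for example the proximal leg box without proximal arm weakness or waddling gait, or the eye or mouth box alone.

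**Effect on the primary count.** A case is a page 1 yes plus a positive antibody test. No page 2 box enters that rule, so the change in the count is 0.

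**Effect on a breakdown of cases.** One misfiled case among 12 moves a proportion by 1/12 = 8.3 percentage points; two move it by 2/12 = 16.7 and three by 3/12 = 25. The documents give no basis for saying how many cases would be ambiguous, so one to three is an illustration and not an estimate.

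**The case against.** The strongest reply is that page 2 only describes subjects already judged suggestive. The secondary objective of relating suspicious symptoms to antibody positivity (section 2.2) can be met from the page 1 judgement. Individual boxes feed exploratory, descriptive work only, and only among subjects rated suggestive. All of this stands, and it is why the point is minor.

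It can also be said that most of page 2 is sound. Eight of 11 items are unmixed, there is a free-text line, and the page 1 question on whether a VGCC test would normally have been ordered gives a partial marker of clinical suspicion. The eye and mouth boxes contain no limb item, so they cannot blur proximal against distal weakness. This stands too: a reader might infer that the form cannot separate the proximal pattern at all, and that is too strong.

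A reader might also infer that these boxes inflate the primary count with autonomic-only or distal complaints. The documents do not support that. Such subjects can become cases, but only through the page 1 judgement and a positive antibody, and they would do so equally with a perfect page 2. Nor are they errors by the protocol's own terms, since section 1.1 and page 1 both list autonomic features of LEMS. One could take the 7–8% antibody positivity in section 1.2 (28 to 32 of 400) and multiply it by an assumed share rated suggestive on non-specific symptoms. That would size the page 1 judgement and not this defect, and no passage supports any particular share.

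None of these replies resolves the leg wording. It conflicts within one page, and no other section says which reading applies.

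**Conclusion.** The point holds as a minor data-capture fault. The two leg items overlap, and two boxes each merge an autonomic symptom with an ocular or bulbar sign. The items concerned may be misclassified in the section 4.3 correlations, and a description of the cases by symptom pattern is limited for subjects whose evidence lies only in these three boxes. The case definition, the expected 12 cases and every other number in the protocol are unaffected.

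The size in practice depends on how many subjects present only through the mixed boxes, which cannot be derived from the documents. The conclusion assumes that the form in Appendix 2 is the one used at the sites and that no separate completion guide defines the leg items; none is mentioned in the protocol.

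**What to change.** 1. Make the leg items mutually exclusive: proximal leg weakness (hip or upper leg) and distal leg weakness (lower leg or foot). Both may be ticked when both are present.
2. Give dry eyes, drooping eyelids, blurred vision, dry mouth and difficulty swallowing separate boxes. Two boxes become five, so 5 − 2 = 3 are added.
3. Optionally, add a supplementary descriptive row for cases with and without a proximal-weakness item, leaving the primary definition unchanged. This row depends on the leg rewording only.

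The cost is a form revision, the matching database change and three more tick boxes, with no additional assessment of the subject. Records made on the current version (Version 1, 28 May 2025) cannot be split afterwards, so the form version should be kept as a variable and those records shown separately in any symptom-level table. The earlier the change, the fewer records are affected.
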